### **Overall (Induction and Maintenance)**

- Any AEs with an onset date of on or after the study drug start date for the entire study (Day 1) and up to 30 days after permanent discontinuation of study drug.
- Any AEs leading to premature discontinuation of study drug.

Summaries (number and percentage of subjects) of TEAEs by SOC and PT will be provided by treatment group. TEAEs will also be summarized by relationship to study drug and severity. In addition, TEAEs leading to premature discontinuation of study drug will be summarized and listed.

#### **8.6.3. Laboratory Evaluations**

Select laboratory data (using conventional units) will be summarized using only observed data. Absolute value and change from baseline at all scheduled time points will be summarized.

Graded laboratory abnormalities will be defined using the grading scheme defined in the CTCAE in [Appendix 5](#).

Incidence of treatment-emergent laboratory abnormalities defined as values that increase at least 1 toxicity grade from baseline at any time post baseline will be summarized by treatment group. If baseline data are missing, then any graded abnormality (ie, at least a Grade 1) will be considered treatment emergent.

#### **8.6.4. Other Safety Evaluations**

Individual data for physical examination findings, prior and concomitant medications and medical history will be provided. Twelve-lead ECGs and vital signs measurements will be listed by subject and summarized by incidence of events/abnormalities or descriptive statistics as appropriate.

## 8.7. Pharmacokinetic Analysis

For each individual study (Cohort A Induction Study, Cohort B Induction Study and Maintenance Study), plasma concentrations of filgotinib and its metabolite GS-829845 will be listed and summarized by treatment group using descriptive statistics (eg, sample size, arithmetic mean, geometric mean, % coefficient of variation, standard deviation, median, minimum, and maximum). Plasma concentrations over time may also be plotted in semi-logarithmic and linear formats as mean  $\pm$  SD and median (Q1, Q3).

For subjects enrolled in the optional PK substudy, pharmacokinetic parameters of filgotinib and its metabolite GS-829845 will be listed and summarized by treatment; and plasma concentrations of the filgotinib and GS-829845 over time will be plotted in semi logarithmic and linear formats as mean  $\pm$  SD and median (Q1, Q3) by treatment.

Exposure-response relationships for efficacy and safety may also be evaluated.

## 8.8. Biomarker Analysis

For each individual study (Cohort A Induction Study, Cohort B Induction Study and Maintenance Study), descriptive statistics of baseline and change in biomarkers will be provided at each sampling time by treatment. To evaluate treatment effect, a mixed-effect analysis of variance model will be used to calculate a point estimate and 2-sided 95% CI for the mean percent change from baseline in biomarker level for each treatment group at individual time points. The estimate and 95% CI of difference in mean percent change from baseline between each filgotinib dose group and placebo will be provided as well.

Exploratory analyses will also be performed to evaluate the association of individual biomarkers, including the systemic or localized inflammatory biomarkers, or combination of biomarkers with clinical outcomes.

Additional exploratory analyses may be described in the Biomarker Analysis Plan (BAP) if necessary.

## 8.9. Sample Size

### 8.9.1. Induction Studies (Cohorts A and B)

The sample size was chosen to ensure that a clinically meaningful difference in EBS remission rate at Week 10 could be detected when comparing filgotinib to placebo within each Induction Study.

A sample size of 130 subjects in the placebo group and 260 subjects in each filgotinib dose group (n = 650 total per cohort) will provide 90% power for each filgotinib dose group comparison to placebo at a 2-sided 0.025 significance level to detect a treatment difference in EBS remission rate of 15% (25% on filgotinib and 10% on placebo).

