### 3.3. Study Treatments

Based on protocol eligibility criteria, subjects will be screened for enrollment in *either* Cohort A or Cohort B.

Subjects who meet protocol eligibility criteria will be assigned to the respective Cohort and subsequently randomized in a blinded fashion in a 2:2:1 ratio to 1 of 3 treatments as follows:

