#### Treatment Groups (Induction Study)

**Treatment Group 1 (n = 260):** filgotinib 200 mg and placebo-to-match (PTM) filgotinib 100 mg, once daily

**Treatment Group 2 (n = 260):** filgotinib 100 mg and PTM filgotinib 200 mg, once daily

**Treatment Group 3 (n = 130):** PTM filgotinib 200 mg and PTM filgotinib 100 mg, once daily

Note: US and Korea males who have not failed at least two biologic therapies (any TNF $\alpha$  antagonist and vedolizumab) will be randomized in a 2:1 ratio to either filgotinib 100 mg or matching placebo.

Within each Cohort, treatment assignments will be stratified according to the following factors in the Induction and Maintenance studies:

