### **Induction Studies (Cohorts A and B)**

For each individual study (Cohort A Induction Study, Cohort B Induction Study, and Maintenance Study), a Bonferroni approach with equal alpha allocation of 0.025 (2-sided) to each filgotinib dose group comparison with placebo will be used to control the overall study-wide type I error rate at 0.05 within each study. To protect the integrity of the study due to the unblinded interim futility analysis planned for each induction study (Cohort A and Cohort B) (details in Section 8.10), an alpha of 0.00001 will be spent for each filgotinib dose group comparison to placebo within each induction study. As a result, a nominal p-value of less than 0.02499 (2-sided) will be needed to declare statistical significance for the final primary analysis of each filgotinib dose group when compared to placebo to control the study-wise type I error rate at 0.05. If one filgotinib dose group is discontinued for futility at the interim futility analysis, the overall alpha error rate stays unchanged at a 2-sided 0.02499 level for the continuing filgotinib dose group at the primary analysis.

The hypotheses to be tested for the induction studies are outlined below.

The primary null hypotheses to be tested:

- H1: The EBS remission rate in the filgotinib 200 mg group is equal to the EBS remission rate in the placebo group at Week 10
- H2: The EBS remission rate in the filgotinib 100 mg group is equal to the EBS remission rate in the placebo group at Week 10

The key secondary null hypotheses to be tested:

- H3: The MCS remission rate in the filgotinib 200 mg group is equal to the MCS remission rate in the placebo group at Week 10
- H4: The MCS remission rate in the filgotinib 100 mg group is equal to the MCS remission rate in the placebo group at Week 10
- H5: The endoscopic subscore of 0 rate in the filgotinib 200 mg group is equal to the endoscopic subscore of 0 rate in the placebo group at Week 10
- H6: The endoscopic subscore of 0 rate in the filgotinib 100 mg group is equal to the endoscopic subscore of 0 rate in the placebo group at Week 10
- H7: The Geboes histologic remission rate in the filgotinib 200 mg group is equal to the Geboes histologic remission rate in the placebo group at Week 10
- H8: The Geboes histologic remission rate in the filgotinib 100 mg group is equal to the Geboes histologic remission rate in the placebo group at Week 10

[figure not shown]

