### 8.9.2. Maintenance Study

Assuming an induction response rate (ie, proportion of subjects achieving EBS remission or MCS response at Week 10) of 55% among subjects receiving filgotinib 200 mg or filgotinib 100 mg treatment, approximately 285 subjects from each filgotinib dose group from Cohorts A and B Induction Studies combined would be eligible to be re-randomized into the Maintenance Study.

The sample size was chosen to ensure that a clinically meaningful difference in EBS remission rate at Week 58 could be detected when comparing each filgotinib dose group (200 mg or 100 mg) to placebo in the Maintenance Study. A sample size of 95 subjects in the placebo group and 190 subjects in the filgotinib group at the same dose level as the induction dose will provide more than 85% power for each filgotinib dose group comparison to placebo at a 2-sided 0.025 significance level to detect a treatment difference in maintenance EBS remission rate of 20% (40% on filgotinib and 20% on placebo).

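### The planned arm sizes and the 285 re-randomisable 200 mg responders ignore the rule that keeps some US and Korea males off 200 mg, so the stated 200 mg Maintenance power is overstated by an amount the plan does not give

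*Protocol*

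**What the plan says.** Protocol 3.3 has subjects in each cohort "randomized in a blinded fashion in a 2:2:1 ratio to 1 of 3 treatments as follows", with 260, 260 and 130 listed for 200 mg, 100 mg and placebo. A note under the same list says that US and Korea males who have not failed at least two biologic therapies (a TNFα antagonist and vedolizumab) "will be randomized in a 2:1 ratio to either filgotinib 100 mg or matching placebo". Protocol 6.1 and SAP 1.2.1 repeat both the sizes and the note.

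Protocol 8.9.1 and SAP 1.3 base power on the unrestricted sizes: "A sample size of 130 subjects in the placebo group and 260 subjects in each filgotinib dose group (n = 650 total per cohort"). Both sections put the Induction power for either dose against placebo at 90%, for remission rates of 25% and 10% and a two-sided α of 0.025. Protocol 8.9.2 and SAP 1.3 then assume a 55% induction response rate, so that "approximately 285 subjects from each filgotinib dose group from Cohorts A and B Induction Studies combined would be eligible". With 190 filgotinib and 95 placebo subjects per dose, and 40% versus 20% in remission, the design "will provide more than 85% power for each filgotinib dose group comparison to placebo".

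Three other provisions matter:

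- Protocol 4.3.2 excludes any prior TNFα antagonist or vedolizumab use from Cohort A, so every US or Korea male in Cohort A is restricted.
- SAP 6.2.3 tests 200 mg against placebo in Maintenance only among subjects induced on 200 mg.
- SAP 6.2.4.4 acknowledges an imbalance, for Cohort B only. It plans an analysis that removes these males from placebo and makes that analysis primary for 200 mg in Cohort B for a Japanese application.

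**The concern.** The sizes and the allocation note sit together in Protocol 3.3 and agree only if no restricted male enrols. Each restricted male is one subject fewer who could go to 200 mg and one more split between 100 mg and placebo. The sample-size sections neither mention the rule nor give an expected share of such males.

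What is at stake is how the 200 mg results are read. In Maintenance, a 200 mg result that misses significance would be judged against a power that the trial's own allocation rule may not deliver. The same applies to the Japanese primary analysis in Cohort B, for which no power is stated at all.

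**Working it through.** **Inputs.** The documents give 650 per cohort, 2:2:1 allocation (2:1 without 200 mg for restricted males), Induction rates of 25% and 10%, 55% response, 2:1 re-randomisation within dose, Maintenance rates of 40% and 20%, and two-sided α = 0.025 (z = 2.2414). The restricted share s is an assumption. The same s is used in both cohorts. With equal cohorts, Maintenance depends on the average of the two shares.

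**Method.** Two-proportion normal approximation: power = Φ[(d − z·SE0)/SE1], where SE0 uses the pooled rate and SE1 the separate rates. The continuity-corrected version replaces d by d − (1/n1 + 1/n2)/2. Corrected values are in brackets below.

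**Plan's own figures (s = 0).**

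- Induction, 260 v 130: SE0 = 0.04297, SE1 = 0.03760, so (0.15 − 0.0963)/0.0376 = 1.428 and power is 92.3%. The correction takes off 0.0058, giving 1.275 and 89.9%. The stated 90% is therefore matched by the corrected formula. The final-analysis threshold ("a nominal p-value of less than 0.02499 (2-sided) will be needed to declare statistical significance") makes no visible difference.
- Responders: 0.55 × 520 = 286, which matches about 285.
- Maintenance, 190 v 95: 89.2% (86.3%). With 286 responders split 2:1 it is 89.3% (86.4%). Both are consistent with more than 85%.

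**Expected sizes with restricted share s, per cohort.**

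- 200 mg: 260(1−s)
- 100 mg: 260(1−s) + 650s × 2/3
- Placebo: 130(1−s) + 650s/3
- 200 mg responders, both cohorts: 286(1−s)

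| s | 200 mg / 100 mg / placebo | 200 mg responders | Maintenance power, 200 mg | Induction FAS power, 200 mg | Induction power, restricted males removed from placebo |
|---|---|---|---|---|---|
| 0 | 260 / 260 / 130 | 286 | 89.3% (86.4%) | 92.3% (89.9%) | 92.3% (89.9%) |
| 5% | 247 / 269 / 134 | 272 | 87.5% (84.2%) | 92.5% (90.1%) | 90.8% (87.9%) |
| 10% | 234 / 277 / 139 | 257 | 85.4% (81.7%) | 92.6% (90.2%) | 88.9% (85.6%) |
| 20% | 208 / 295 / 147 | 229 | 80.4% (75.6%) | 92.4% (90.0%) | 84.3% (79.8%) |
| 30% | 182 / 312 / 156 | 200 | 74.0% (68.0%) | 91.8% (89.4%) | 78.1% (72.3%) |

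The last column uses 260(1−s) against 130(1−s).

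**Crossing points.** Maintenance power for 200 mg reaches 85% at s of about 11% uncorrected (286 × 0.89 ≈ 255 responders), or about 3.3% corrected (286 × 0.967 ≈ 277 responders). Induction FAS power does not fall below its s = 0 value until s is about 22% (23% corrected). With restricted males removed from placebo, uncorrected Induction power passes below 90% at s of about 7%.

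The 100 mg dose is not harmed. At s = 10% its responders would be about 0.55 × 2 × 277.3 = 305.

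**The case against.** A reader might infer that the stated 90% Induction power for 200 mg is lost. The documents do not support that. The primary analysis uses the FAS, which keeps the restricted males in placebo. The larger placebo arm offsets the smaller 200 mg arm, and power holds at about 90% up to s of about 20%. One condition attaches: the added placebo subjects must also remit at 10%. SAP 6.2.4.4 itself raises the possibility that such subjects respond better, which would lower this power.

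Nor do the documents show that the stated sizes are impossible. Enrolment per cohort and the responder count are both given as approximate, so a very small s would fit. The power sentences are also correct for the sizes they name.

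The imbalance is acknowledged in SAP 6.2.4.4. That section covers Cohort B only, though, and leaves the sample-size text untouched.

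For Maintenance, the fair reply is that s is unknown. The planned test is a stratified CMH chi-square, and SAP 6.2.3 specifies continuity correction only for the confidence intervals. On the uncorrected scale the claim of more than 85% survives to s of about 11%. That stands as a reason to show both scales. It does not remove the point, because the corrected formula is the one that matches the planned 90%, and on either scale Maintenance power falls steadily as s rises.

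**Conclusion.** The point holds in a limited form. The sizes 260/260/130 and the figure of about 285 responders on 200 mg rest on 2:2:1 allocation for everyone, which the plan's own rule contradicts. The direction is certain for any s above zero; the size depends on s.

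The stated power affected is Maintenance at 200 mg: about 4 percentage points lower at s = 10% (89.3% to 85.4%) and about 9 lower at s = 20% (89.3% to 80.4%), uncorrected. The Cohort B analysis in SAP 6.2.4.4 also loses power, but the documents state none for it.

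These figures hold the planned remission and response rates fixed and assume equal cohorts with a common s. Cohort A restricts all its US and Korea males and Cohort B only some, so the two shares will probably differ.

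**What to change.** In Protocol 3.3, 8.9.1 and 8.9.2 and SAP 1.2.1 and 1.3 (and Protocol 6.1, which repeats the sizes):

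- State the projected share of restricted males for each cohort.
- Replace 260/260/130 and the 200 mg responder count with expected values under the mixed 2:2:1 and 2:1 allocation.
- Restate the 200 mg Maintenance power for the resulting number of responders.
- Give the 200 mg Induction power twice: for the FAS, and for the SAP 6.2.4.4 analysis.
- Say which power formula is used, since the corrected and uncorrected versions cross 85% at very different shares.

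The cost is a change of text. The sponsor must supply its projected share, which the documents do not contain, and the stated 200 mg Maintenance power becomes less favourable. No extra enrolment and no change to the allocation rule or the planned tests is asked for.

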### 8.9.2. Maintenance Study

Assuming an induction response rate (ie, proportion of subjects achieving EBS remission or MCS response at Week 10) of 55% among subjects receiving filgotinib 200 mg or filgotinib 100 mg treatment, approximately 285 subjects from each filgotinib dose group from Cohorts A and B Induction Studies combined would be eligible to be re-randomized into the Maintenance Study.

The sample size was chosen to ensure that a clinically meaningful difference in EBS remission rate at Week 58 could be detected when comparing each filgotinib dose group (200 mg or 100 mg) to placebo in the Maintenance Study. A sample size of 95 subjects in the placebo group and 190 subjects in the filgotinib group at the same dose level as the induction dose will provide more than 85% power for each filgotinib dose group comparison to placebo at a 2-sided 0.025 significance level to detect a treatment difference in maintenance EBS remission rate of 20% (40% on filgotinib and 20% on placebo).

### 8.10. Data Monitoring Committee

An external DMC will review the progress of the study and perform interim reviews of safety data and provide recommendation to Gilead whether the nature, frequency, and severity of adverse effects associated with study treatment warrant the early termination of the study in the best interests of the participants, whether the study should continue as planned, or the study should continue with modifications.

The initial meeting for each induction study will occur after approximately 100 subjects (20 from placebo group and 40 from each filgotinib group) reach Week 10.

The second meeting for each induction study will include an interim futility analysis and occur after approximately 175 subjects (35 from placebo group and 70 from each filgotinib treatment group) reach Week 10. The futility analysis will be conducted to evaluate endoscopic efficacy and overall safety. The proportion of subjects who achieve endoscopic response (endoscopic subscore of 0 or 1) for each treatment group will be evaluated. The DMC may recommend to terminate a filgotinib dose group if the observed proportion of subjects who achieve endoscopic response in the filgotinib group is lower than that in the placebo group. If both filgotinib dose groups meet the futility criteria, the DMC may recommend stopping the study.

After the futility analyses, DMC meetings for safety review will be held approximately once every 4 months or at a frequency determined by the DMC.

The DMC's specific activities will be defined by a mutually agreed charter, which will define the DMC's membership, conduct and meeting schedule.

While the DMC will be asked to advise Gilead regarding future conduct of the study, including possible early study termination, Gilead retains final decision-making authority on all aspects of the study.

### **Cohorts A and B End-of-Induction Analysis**

Efficacy and safety data will be evaluated by DMC after *all* subjects in both cohorts complete Week 10 dosing (or prematurely discontinue study drug but complete post-treatment assessments).

Both cohorts will be examined independently.

- Taking into account data in Cohort A and Cohort B, if both filgotinib dose groups (200 mg and 100 mg) in both cohorts (independently examined) fail to reach statistical significance compared to placebo on EBS remission, the DMC may recommend overall study discontinuation.
- If the above condition above is not met, the DMC may recommend that the study continue without modification.

### **Ad-hoc DMC Meetings**

An ad-hoc convening of DMC may be triggered by the following conditions:

- $\geq 2$  subjects develop the same (by preferred term) related, Grade 4, unexpected adverse event (AE) in the infections and infestations system organ class
- Any subject develops a Grade 5, related, unexpected AE. The definition of an unexpected AE will be based on the Reference Safety Information that is on file at the time the event occurs.

### **8.11. End of Induction Interim Analysis**

After all subjects from Cohorts A and B have completed the Week 10 visit or have terminated prior to Week 10 and corresponding data entry is complete, an End of Induction safety and efficacy analysis will be performed including cumulative safety analysis that has been provided for DMC safety review and analyses on primary endpoint and key secondary endpoints as well endoscopic response and MCS response.

In parallel with DMC review, a prespecified sponsor's executive team will review the unblinded group level safety analysis results and group level efficacy analysis results from the Induction Studies for the purpose of sponsor decision making and future development planning. Members of the Study Management Team with direct involvement in the conduct of the study will not have access to the unblinded results from the induction studies.

The unblinded End of Induction analysis results of Study GS-US-418-3898 will not be shared externally with the exception of Health Authority or DMC requests for information, until after the Week 58 database lock is completed and the study is unblinded.

Follow up actions may be taken based on the data from this analysis including study design change, with communication with regulatory authorities, if indicated.

Further details will be specified in the SAP and an Interim Analysis Communication Plan.

## **9. RESPONSIBILITIES**

### **9.1. Investigator Responsibilities**

#### **9.1.1. Good Clinical Practice**

The investigator will ensure that this study is conducted in accordance with the principles of the Declaration of Helsinki, International Council for Harmonisation (ICH) guidelines, or with the laws and regulations of the country in which the research is conducted, whichever affords the greater protection to the study subject. These standards are consistent with the EU Clinical Trials Directive 2001/20/EC and GCP Directive 2005/28/EC.

The investigator will ensure adherence to the basic principles of GCP, as outlined in 21 CFR 312, subpart D, "Responsibilities of Sponsors and Investigators," 21 CFR, part 50, and 21 CFR, part 56.

The investigator and all applicable subinvestigators will comply with 21 CFR, Part 54, providing documentation of their financial interest or arrangements with Gilead, or proprietary interests in the investigational drug under study. This documentation must be provided prior to the investigator's (and any subinvestigator's) participation in the study. The investigator and subinvestigator agree to notify Gilead of any change in reportable interests during the study and for 1 year following completion of the study. Study completion is defined as the date when the last subject completes the protocol-defined activities.

#### **9.1.2. Institutional Review Board/Independent Ethics Committee Review and Approval**

The investigator (or sponsor as appropriate according to local regulations) will submit this protocol, ICF, and any accompanying material to be provided to the subject (such as advertisements, subject information sheets, or descriptions of the study used to obtain informed consent) to an IRB/IEC. The investigator will not begin any study subject activities until approval from the IRB/IEC has been documented and provided as a letter to the investigator.

Before implementation, the investigator will submit to and receive documented approval from the IRB/IEC any modifications made to the protocol or any accompanying material to be provided to the subject after initial IRB/IEC approval, with the exception of those necessary to reduce immediate risk to study subjects.

